## 6. ANALYSIS POPULATIONS

For the analysis, the following populations are defined:

**Table 3. Analysis Populations**

Population	Description
Screened	All subjects who sign the main study informed consent form.
Screen Failures	A subject who signs the informed consent but has not received any dose of SL-279252.
All Treated	All subjects who receive at least one dose of SL-279252. Safety data will be evaluated based on this population.
DLT Evaluable	All subjects in the dose escalation cohorts and All Treated Population who receive at least 2 doses of SL-279252 for Schedule 1 and at least 3 doses for Schedule 2 during the DLT evaluation period, complete the safety follow up through DLT evaluation period or experience any DLT during the DLT evaluation period. The DLT evaluation period is defined as the first 21 days or 28 days of treatment on Schedule 1 or Schedule 2, respectively.
Efficacy Evaluable	All subjects in the All Treated Population who received at least 3 doses of SL-279252 and had at least one disease assessment or had progressed or died before the first post-baseline disease assessment.
Immunogenicity Population	All subjects in the All Treated Population who had at least one evaluable immunogenicity assessment.

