		
  
 Grade 3	 
 Immediately discontinue infusion. Begin IV infusion of normal saline and treat with epinephrine, bronchodilators, diphenhydramine, ranitidine, corticosteroids, oxygen, fluids, vasoressors etc. as indicate and per institutional guidelines. Epinephrine is the drug of choice in an anaphylactic reaction and its administration should not be delayed. Admit to hospital for close observation until resolution of symptoms. Rechallenge should not be attempted in cases of true anaphylaxis. In other cases, once subject has completely recovered, carefully consider if it is safe for the subject to receive IP at the next scheduled dose with pre-medication (e.g., corticosteroids, anti-histamines, antipyretics) and slow infusion ($\leq 50\%$ of the rate at which the reaction occurred). If no further symptoms, rate may be escalated at intervals and increments as clinically appropriate. If symptoms recur, permanently discontinue IP 	
  
	Grade 3	
 Immediately discontinue infusion. Begin IV infusion of normal saline and treat with epinephrine, bronchodilators, diphenhydramine, ranitidine, corticosteroids, oxygen, fluids, vasoressors etc. as indicate and per institutional guidelines. Epinephrine is the drug of choice in an anaphylactic reaction and its administration should not be delayed. Admit to hospital for close observation until resolution of symptoms. Rechallenge should not be attempted in cases of true anaphylaxis. In other cases, once subject has completely recovered, carefully consider if it is safe for the subject to receive IP at the next scheduled dose with pre-medication (e.g., corticosteroids, anti-histamines, antipyretics) and slow infusion ($\leq 50\%$ of the rate at which the reaction occurred). If no further symptoms, rate may be escalated at intervals and increments as clinically appropriate. If symptoms recur, permanently discontinue IP

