9.3 Populations for Analyses

For the analysis, the following populations are defined:

Population	Description
Enrolled	All subjects who sign the main study ICF.
Screen Failures	A subject who signs the informed consent but has not received any dose of SL-279252
All Treated	All subjects who receive at least one dose of SL-279252. Safety data will be evaluated based on this population.
DLT Evaluatable	All subjects in the All Treated population who receive at least 2 doses of SL-279252 for Schedule 1 or at least 3 doses for Schedule 2, complete the safety follow up through DLT evaluation period or experience any DLT during the DLT evaluation period. The DLT evaluation period is defined as the first 21 days or 28 days of treatment on Schedule 1 or Schedule 2, respectively. Evaluatable subjects will be used to guide dose escalation and to determine the MTD or MAD.
Evaluatable for Efficacy	A subject who received at least 3 doses of SL-279252 and had at least one post-baseline disease assessment or had progressed or died before the first post-baseline disease assessment. .
Pharmacokinetic	All subjects in the All Treated population who received at least one dose of SL-279252 and have at least one evaluable post-dose sample collected. The PK population will be used for PK analysis.
Pharmacodynamic	All subjects in the All Treated population for whom sufficient samples are available for the analysis. The pharmacodynamic population will be used for the pharmacodynamic data analysis.

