14. DATA HANDLING AND RECORD KEEPING

14.1 Communication and Data Dissemination Plan

During the study while subjects are receiving treatment with SL-279252, SMC meetings will be held to review relevant data with the investigators or delegates. These meetings will be held once a month (or more frequently if required) during dose escalation to share safety data and communicate results of ongoing analyses. Available safety, PK, pharmacodynamic, and clinical outcome data for all subjects at the time of the scheduled SMC Meeting will be reviewed and summarized. Attendees of SMC meetings will include but not be limited to clinical investigators (or designees), the Sponsor Medical Monitor and Statistician.

The Sponsor will remain in constant contact with the clinical sites during the enrollment period to ensure that cohort enrollment during the dose escalation or dose expansion phases of this study are completed as per protocol. Investigators will be informed about available openings for enrollment on the trial and will be asked to pre-screen subjects to determine their potential for eligibility to avoid over-enrollment. Enrollment will be offered to all sites and slots filled based on the Keyboard Design method.

Dose escalation decisions will be made based on the DLTs observed at the current dose level with guidance provided by the Keyboard design as stated in the study protocol. All dose escalation and dose expansion or safety decisions will be documented in writing with copies maintained at each site and the Trial Master File at the CRO.

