- There will be a 3-day stagger between the first and second subjects enrolled at a given dose level. **NOTE:** This requirement may change based on emerging data as per the SMC.
- The column corresponding to the total number of evaluable subjects treated at the current dose level should be used to make the appropriate decision (i.e., escalate, stay at the same dose, de-escalate or eliminate).
- If a subject is not evaluable, a decision can still be made based on the total number of subjects who are evaluable at the current dose without enrolling an additional subject (unless all subjects in a cohort are not evaluable*).
- More than 3 subjects may be enrolled in a cohort if additional subject(s) are available for dosing after consultation with the Sponsor.

***NOTE:** If all subjects in a cohort are not evaluable, an additional cohort should be enrolled at the same dose level.

Dose escalation for schedule 1 may continue until:

- The trial is stopped for safety **OR**
- The maximum sample size of 42 subjects is reached **OR**
- The maximum sample size has not been reached but 12 subjects have been enrolled at the current dose level **OR**

- The Sponsor, in consultation with the SMC, decides to stop enrollment in schedule 1 early (e.g., based on safety, pharmacodynamics) and begin enrollment in schedule 2 (see Section 3.2.7)

NOTE: The maximum sample size of 42 may be revised if additional dose levels are evaluated or if more additional subjects (i.e., subjects available for dosing beyond the number required in a cohort) are enrolled than anticipated. The Sponsor, in consultation with the SMC, may also elect to add subjects if additional safety data are needed to select a dose and schedule for the expansion cohorts. Six (6) subjects must be treated at a dose level to confirm safety and tolerability before a dose can be used in an expansion cohort.

16.3.1.2 Dose Escalation – Schedule 2

See Section 3.2.4 for the dose levels to be evaluated if schedule 2 is opened.

Subjects will be enrolled in cohorts of 3, with the table in Section 16.3.1 used to guide dose escalation.

- There will be a 3-day stagger between the first and second subjects enrolled at a given dose level. **NOTE:** This requirement may change based on emerging data as per the SMC.

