toxicities that result in subjects not receiving at least ~~6650%~~ of the scheduled dose during the DLT assessment period may be taken into consideration when assessing the totality of the data in determining evaluability for DLT and the RP2D.

Section 9.3 in the table that includes populations for Analyses the DLT Evaluable population is defined as (new text in italics): All subjects in the All Treated population who receive at least 2 doses of SL-279252 *for Schedule 1 or at least 3 doses for Schedule 2*, complete the safety follow up through DLT evaluation period or experience any DLT during the DLT evaluation period. The DLT evaluation period is defined as the first 21 days or 28 days of treatment on Schedule 1 or Schedule 2, respectively. Evaluable subjects will be used to guide dose escalation and to determine the MTD or MAD.

16.15 Summary of Protocol Changes – Amendment 07

Minor Editorial Changes:

Document Headers

Updated to denote version 07 of protocol

Title page

Approval date changed to 12 July 2021 and protocol version number changed to version 07

Rational for Global Amendment 06

Minor editorial changed noting summary provided for Amendment 06 ~~05~~

Rational for Global Amendment 07 added

Abbreviations list

Added TPS and CPS to abbreviations list

Table of Contents

Updated to include new Appendix Section 16.15

Page numbers revised

Synopsis

Revised inclusion criterion #2 to align with text changes made in the main body of the protocol as described below.

Added new inclusion criterion #3 to align with text changes made in main body of the protocol as described below.

Revised exclusion criterion #2 to align with text changes made in main body of the protocol as described below

1) Institute requirement that eligible subjects have tumors with PD-L1 expression $\geq 1\%$ according to tumor TPS or CPS at baseline.

- Section 1.3 Rationale; new text (italics) added as shown below:

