### 11.1 Maximum Tolerated Dose Evaluation

The MTD evaluation will be based on the DLT Evaluable Population. The number and percentage of subjects with DLT during the dose escalation phase will be presented by dose level and schedule. The MTD level will be indicated in the summary as appropriate. For single subject cohorts, qualifying  $\geq$  Grade 2 toxicities that trigger a change to at least 3 subject cohorts will also be specified in the table footnotes.

The MTD will be estimated using isotonic regression (based on the DLTs observed in the DLT evaluable subjects). A MAD will be reported if a schedule is fully evaluated, but the DLT rate is less than 25% for all dose levels. Otherwise, an MTD will be reported. Isotonic regression is a way to estimate the MTD under the assumption that toxicity increases with dose. When using isotonic regression, the first step is to identify the doses where the dose-toxicity monotonicity assumption is violated. The DLT estimate is then adjusted for the violators such that the final estimate of the DLT rate increases with the dose. The target DLT rate is then used to select the MTD. For example, suppose that when the trial is completed, the observed DLT rates [<# subjects who experienced DLT]/[# evaluable subjects] at five dose levels are (0/3, 1/3, 0/3, 4/15, 2/4). In this example the observed DLT rate at Dose Level 2 (i.e., 1/3=33%) is higher than the observed DLT rate at Dose Level 3 (i.e., 0/3=0%). To adjust for this violation, the DLT estimates are replaced with their average, i.e.,  $(1/3+0/3)/2=1/6$ , resulting in the isotonic regression DLT estimates (0/3, 1/6, 1/6, 4/15, 2/4) = (0%, 16.7%, 16.7%, 26.7%, 50%), which monotonically increases with the dose level. Based on this isotonic estimate, assuming that the trial goal is to find the dose with the DLT rate of 30%, Dose Level 4 will be selected as the MTD. If there are no violators of the dose-toxicity monotonicity assumption, isotonic regression directly uses the observed DLT rates as the final estimates for MTD selection. For subjects who undergo intra-subject dose escalation, only DLTs that occur during the DLT period on the subject's initial dose will be used for MTD determination.

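### The DLT Evaluable definition is ambiguous: one reading drops a DLT that ends dosing early, another counts DLT-free subjects who never finished the DLT period

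*SAP*

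**What the plan says.** SAP Table 3 limits the population to treated subjects in the dose escalation cohorts "who receive at least 2 doses of SL-279252 for Schedule 1 and at least 3 doses for Schedule 2 during the DLT evaluation period", and then adds, after a comma, "complete the safety follow up through DLT evaluation period or experience any DLT during the DLT evaluation period". Protocol 9.3 has the same construction: "receive at least 2 doses of SL-279252 for Schedule 1 or at least 3 doses for Schedule 2, complete the safety follow up", and so on to the DLT limb. Neither text joins the dose clause to the rest with an explicit *and*, and neither says whether a DLT counts regardless of the doses received.

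The population carries the primary dose-escalation result. Protocol 9.3 states: "Evaluable subjects will be used to guide dose escalation and to determine the MTD or MAD". SAP 11.1 states: "The MTD evaluation will be based on the DLT Evaluable Population". Protocol 16.3.1.1 sets the Keyboard denominator the same way: "The column corresponding to the total number of evaluable subjects treated at the current dose level should be used to make the appropriate decision". The SAP's planned DLT table (14.3.1.11) and DLT listing (16.2.7.2) are also restricted to DLT Evaluable subjects.

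**The concern.** Some events that meet the DLT definition end treatment at once. Protocol 3.5.1 permanently stops the product for a Grade 4 infusion reaction and for Grade 4 CRS, and says "Rechallenge should not be attempted in cases of true anaphylaxis". If such an event follows dose 1, the subject never reaches 2 or 3 doses. On Schedule 2 the same gap covers a DLT after dose 2.

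If the dose minimum binds these subjects, each leaves both the numerator and the denominator. Protocol 16.3.1.1 then lets the decision go ahead without replacing them, and Scenario #3 in 16.3.1.3 shows exactly this: one of three subjects is not evaluable, 0 of the other 2 has a DLT, and the dose is escalated. The error runs in one direction, towards a lower apparent DLT rate and a higher MTD.

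**Working it through.** **1. The readings.** The comma and the *or* allow three.

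| Reading | DLT after dose 1, no further dose | Minimum doses, no DLT, follow-up not completed |
|---|---|---|
| A: doses AND (follow-up OR DLT) | excluded | excluded |
| B: (doses AND follow-up) OR DLT | counted | excluded |
| C: any one of the three | counted | counted as DLT-free |

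Only B handles both subjects sensibly. Two features of SAP Table 3 lend A some support. The SAP ties the dose count to the DLT period, so that it stands as a condition of its own. The next row, Efficacy Evaluable, has the same shape with an explicit *and* after its dose minimum.

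**2. Whether other sections settle it.**
- Protocol 14.1 leans towards counting every DLT: "Dose escalation decisions will be made based on the DLTs observed at the current dose level with guidance provided by the Keyboard design". But that guidance works through evaluable subjects.
- Protocol 3.2.6 addresses toxicity that leaves a subject below 66% of the scheduled dose (2 of 3 doses = 66.7%; 3 of 4 = 75%), but says only that this may be considered in judging evaluability.
- SAP section 12 comments on this population only to confine it to the dose escalation cohorts.

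**3. Single decisions.** From the Keyboard table (protocol 16.3.1, SAP Table 1), removing one subject with a DLT turns d/n into (d−1)/(n−1):

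| All DLTs counted | One early DLT lost |
|---|---|
| 1/3 stay | 0/2 escalate |
| 2/6 stay | 1/5 escalate |
| 2/5 de-escalate | 1/4 stay |
| 3/3 eliminate | 2/2 de-escalate |
| 4/6 eliminate | 3/5 de-escalate |
| 2/3 de-escalate | 1/2 de-escalate (unchanged) |
| 3/6 de-escalate | 2/5 de-escalate (unchanged) |
| 3/9 stay | 2/8 stay (unchanged) |

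**4. Apparent DLT rate.** With true rate p and a share f of DLT subjects lost, the apparent rate is p(1−f)/(1−pf). The documents give no value for f, so it is an assumption. At p = 0.30:
- f = 0.10: 0.27/0.97 = 27.8%
- f = 0.20: 0.24/0.94 = 25.5%
- f = 0.30: 0.21/0.91 = 23.1%, below the 25% lower edge of the target range

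**5. The plan's own operating characteristics.** I used the printed table, cohorts of 3, a stop at 12 subjects per dose, the elimination rule, an isotonic MTD closest to 0.30, and 5,000 trials per scenario. With every DLT counted, the true MTD is selected in:
- Schedule 2, scenarios 1 to 4: 65.8, 50.7, 53.8 and 51.5% (protocol 9.2.1.2: 64.36, 49.9, 54.24 and 51.84%)
- Schedule 1, scenarios 1, 4 and 6: 57.2, 47.4 and 45.6% (protocol 9.2.1.1: 57.7, 47.86 and 45.48%)

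All are within 2 points. In Schedule 2 scenario 1, a dose above the true MTD is selected in 21.1% of trials, against 18.02 + 4.06 + 0.26 = 22.34% in the protocol.

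**6. Effect of losing early DLTs.** These runs use Schedule 1 scenarios 1 to 8 with the single-subject start and an assumed 10% chance of a qualifying Grade 2 event. Each entry is the range across scenarios of the percentage selecting a dose above the true MTD. Repeat runs agree within about 2 points.

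| Share of DLTs lost (assumed) | Lost from live decisions and final estimate | Lost from final estimate only |
|---|---|---|
| 0 | 13-27% | 13-27% |
| 10% | 18-34% | 15-32% |
| 20% | 25-41% | 17-33% |
| 30% | 32-50% | 19-35% |

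Reading C is not simulated, because the documents give no rate of incomplete follow-up. Its direction is clear: it adds DLT-free subjects with incomplete observation, and so also lowers the apparent DLT rate.

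**The case against.** A reader might infer that the text, taken literally, requires early DLTs to be excluded. It does not. Reading B is equally open and keeps every DLT, and protocol 14.1 points that way. The DLT rate in protocol 9.4.1.1 and SAP 11.1 is described as subjects with a DLT over evaluable subjects, with no dose minimum on the numerator. Protocol 16.3.1.1 expands a single-subject cohort on any DLT, again with no minimum.

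A reader might also take 32-50% as the expected effect. That range needs 30% of DLTs to be early and the SMC, which makes escalation decisions under SAP 3.2, to disregard a severe reaction that it has reviewed. Loss at the programming stage is easier to imagine, and its effect is much smaller. Live exclusion still cannot be ruled out, since protocol 9.3 says that evaluable subjects guide escalation.

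Three further limits stand:
- Protocol 3.5.1 allows rechallenge after Grade 3 CRS and after some Grade 3 infusion reactions, so some of these subjects may still reach the minimum.
- In the monkey studies, reactions began at the third dose or later (protocol 1.2.4 and 3.2.3). Timing in humans is unknown, so first-dose events are possible but not shown to be common.
- An excluded DLT would remain in the general adverse event outputs, which use All Treated, and RP2D selection reviews all safety data.

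None of this removes the ambiguity. It limits how often the ambiguity would matter and how far it would shift the result.

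**Conclusion.** The definition is ambiguous, and two of its three readings give a wrong count. It supports the primary dose-escalation result, and under either wrong reading the error favours a higher MTD. The documents do not compel exclusion of early DLTs, and the likely intent is to count them.

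Under reading A, the rise in over-selection is modest if only the final estimate is affected (to 19-35% at the largest share considered, from 13-27%) and large if live decisions follow the same reading (to 32-50%). Both figures rest on an assumed share of early DLTs, the printed Keyboard table and the protocol's own toxicity scenarios. Because the change costs so little, it should be made before the population is programmed.

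**What to change.** Replace the definition in SAP Table 3 and protocol 9.3 with:

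*All Treated subjects in the dose escalation cohorts who EITHER have a DLT during the DLT evaluation period, regardless of the number of doses received, OR receive at least 2 doses (Schedule 1) or 3 doses (Schedule 2) in that period AND complete safety follow-up through its end without a DLT.*

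Record the clarification in SAP section 12. The cost is one sentence in each document. The DLT criteria, the Keyboard table, the sample size and the treatment rules are unchanged.

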k. **Tumor Assessment:** Tumor assessments are required for all subjects within 28 days prior to enrollment. Baseline and on-treatment tumor assessments for solid tumors by iRECIST should include CT with contrast of chest, abdomen, and pelvis and other known sites of disease at each time point. Bone scan and positron emission tomography (PET)/CT should be performed only if clinically indicated. Baseline and on-treatment tumor assessment for lymphoma by RECIL 2017 should be done using CT scan with contrast and PET/CT of neck, chest, abdomen, and pelvis and other known sites of disease at each time point. Please refer to Section 8 for requirements regarding disease assessment. Tumor assessments must be performed at screening and at the following intervals until disease progression is confirmed: approximately every 8 weeks through week 24 (e.g., C3D1, C5D1, C7D1), every 12 weeks up to year 2 (prior to cycles 10, 13, 16, 19, 22, 25, 28 and 31), and then every 6 months (prior to cycles 37, cycle 43, etc.) up to conclusion of the study. Confirmatory scans should be performed at least 4 weeks (>28 days), but no longer than 8 weeks after initial documentation of an objective response. Subjects who discontinue study treatment for reasons other than disease progression (e.g., AE or withdrawal of consent) will be monitored for radiologic response until start of another anti-cancer therapy, or disease progression, withdrawal of consent or death.

l. **PK/immunogenicity (i.e., ADA) and cytokine sampling (Dose Escalation Cohorts):** PK, ADA, and cytokine time points for collection of samples are outlined in supplementary tables in Section 6.1.1. ([Table 6](#), [Table 7](#) and [Table 8](#)). Blood volumes required are provided in the SLM. PK, ADA, cytokine samples should not be collected from infusion port for drug delivery i.e., recommend having a separate line in the opposite arm for sample collection. If subject has positive ADA test on D1 of cycle 13, then follow up predose samples for PK/ADA should be collected every ~90 days on D1 of subsequent treatment cycles until ADA resolves to baseline. If ADA positivity is detected within 7-30 days after the last dose of SL-279252, then follow up testing for PK/ADA should be performed at monthly intervals until ADA resolves to baseline.

m. **Correlative laboratory studies:** Refer to supplementary [Table 9](#) for details in Section 6.1.2 plus see the SLM for amount of blood needed.

- *Complement*

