8. ANTI-TUMOR ACTIVITY ASSESSMENTS

Although the clinical benefit of SL-279252 has not yet been established, the intent of offering this IP is to provide a possible therapeutic benefit, and thus the participant will be carefully monitored for tumor response and symptom relief in addition to safety and tolerability.

For the purposes of this study, participants should be evaluated for response as outlined in the SOA. Confirmatory scans should be performed at least 4 weeks (>28 days), but no longer than 8 weeks after initial documentation of an objective response. All participants who receive at least 3 doses of SL-279252 and had the first disease assessment at the 8-week time point will be considered evaluable for response.

Assessments must be performed on a calendar schedule and should not be affected by dose interruptions or delays. Refer to the SOA (Section 6) for the schedule of disease assessments. More frequent disease assessments may be performed at the discretion of the investigator. For subjects whose disease may be followed by well-characterized tumor markers, disease assessments should include results of tumor marker assessments. If study treatment is withdrawn for reasons other than disease progression, radiographic disease assessments should continue as per the SOA until documented disease progression, the start of new anti-cancer therapy, withdrawal of consent or death. See Sections 8.3 for criteria for continuing treatment past disease progression.

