## 8. EFFICACY ANALYSES

The efficacy analysis will be based on the All Treated population and/or Efficacy Evaluable population, as appropriate. The efficacy endpoints include ORR, CBR, time to response (TTR), DOR, tumor size change from baseline for target lesions, PFS, and OS.

Response assessment will be based on the iRECIST for solid tumors and RECIL 2017 for lymphoma. Radiographic disease assessment must be performed at screening, and at the following intervals until a disease progression is confirmed: every 8 weeks through week 24, every 12 weeks

up to year 2 and then every 6 months up to conclusion of the study. Disease assessment window is +/- 1 week. Confirmatory assessments should be performed at least 4 weeks ( $\geq$  28 days) after the initial documentation of an objective response or an unconfirmed disease progression. Subjects who discontinue study treatment for reasons other than disease progression will be monitored for radiologic response until start of new anti-cancer therapy, disease progression, withdrawal of consent or death.

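### SAP Table 3 drops post-baseline from the Efficacy Evaluable definition, so read literally a baseline scan qualifies and the Efficacy Evaluable ORR and CBR are slightly diluted

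*SAP*

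**What the plan says.** Three places say who is evaluable for response, and they differ.

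- **Protocol Section 8:** "All participants who receive at least 3 doses of SL-279252 and had the first disease assessment at the 8-week time point" are evaluable. There is no route in for a subject who progresses or dies before that scan.
- **Protocol 9.3, Evaluable for Efficacy:** at least 3 doses, and the subject "had at least one post-baseline disease assessment or had progressed or died before the first post-baseline disease assessment".
- **SAP Table 3, Efficacy Evaluable:** the subject "received at least 3 doses of SL-279252 and had at least one disease assessment or had progressed or died before the first post-baseline disease assessment". This is the 9.3 rule without post-baseline in the assessment clause.

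The footnotes to all four schedule-of-assessments tables (Protocol 6.1 to 6.4) state that "Tumor assessments are required for all subjects within 28 days prior to enrollment".

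SAP 8.1.3, 8.2.3 and 8.3.3 derive best overall response from post-baseline assessments only. SAP 8.1.2, 8.2.2 and 8.4 plan ORR and CBR in both All Treated and Efficacy Evaluable. SAP 8.3.2 does the same for lymphoma if the data allow. SAP Section 12 lists two changes from the protocol, on the Screened and DLT Evaluable populations; neither concerns this one.

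**The concern.** A programmer builds the population flag from the SAP text. If a baseline scan satisfies the assessment clause, that clause removes nobody who was scanned as required, and the population becomes everyone with at least 3 doses. The subjects let in by this are those who stop before any on-treatment scan without progressing or dying. They cannot be classed as responders or as having clinical benefit, so they add to the denominator and never to the numerator. The rate labelled Efficacy Evaluable would then not be the one Protocol 9.3 defines, and the SAP does not declare the departure.

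The Protocol Section 8 sentence is a second inconsistency and works the other way. By requiring the 8-week scan it leaves out early progressions and deaths, which would raise the rate.

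Such subjects are plausible. On either schedule the third dose falls on Day 15, and the first scheduled on-treatment scan is at C3D1, Day 57. That leaves 57 − 15 = 42 days in which a subject has enough doses but no scan.

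**Working it through.** The plan states no efficacy-evaluable N and no assumed response rate, so there is no figure to reproduce. The check applies each definition to each type of subject, then illustrates the denominators. It takes the baseline scan as present, as the protocol requires, and reads the 3-dose condition as applying to both branches of the rule.

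| Subject with at least 3 doses | Protocol 8 | Protocol 9.3 | SAP Table 3 (literal) |
|---|---|---|---|
| A: scanned at week 8 | in | in | in |
| B: only an off-schedule post-baseline scan | out | in | in |
| C: progressed or died before first scan | out | in | in |
| D: no post-baseline scan, no progression or death | out | out | in |

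Only type D separates the SAP from Protocol 9.3. Types B and C separate Protocol 8 from 9.3.

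Let N be the cohort size, L the number with fewer than 3 doses, and B, C and D the counts above. The denominators are:

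- SAP: N − L
- Protocol 9.3: N − L − D
- Protocol 8: N − L − D − C − B
- All Treated: N

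The cohort size of 15 is the planned expansion cohort size in SAP Section 4. All other counts are assumptions.

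**Illustration 1:** N = 15, L = 0, C = 3, D = 1, B = 0, 2 responders.

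- SAP: 2/15 = 13.3% (exact 95% CI 1.7 to 40.5)
- Protocol 9.3: 2/(15 − 1) = 2/14 = 14.3% (1.8 to 42.8)
- Protocol 8: 2/(15 − 1 − 3) = 2/11 = 18.2%
- All Treated: 2/15 = 13.3%

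**Illustration 2:** N = 15, L = 1, C = 2, D = 2, B = 0, 3 responders.

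- SAP: 3/14 = 21.4% (4.7 to 50.8)
- Protocol 9.3: 3/(14 − 2) = 3/12 = 25.0% (5.5 to 57.2)
- Protocol 8: 3/(12 − 2) = 3/10 = 30.0% (6.7 to 65.2)
- All Treated: 3/15 = 20.0% (4.3 to 48.1)

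**Range over D**, with N = 15, L = 1 and 3 responders. The SAP rate stays at 3/14 = 21.4%.

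| D | Protocol 9.3 |
|---|---|
| 0 | 3/14 = 21.4% |
| 1 | 3/13 = 23.1% |
| 2 | 3/12 = 25.0% |
| 3 | 3/11 = 27.3% |

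Time to response and duration of response are also tabulated in Efficacy Evaluable, but only responders enter them, so those estimates do not move. PFS and OS use All Treated.

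**The case against.** The best defence is that this is a one-word slip which the sentence itself exposes. The second branch covers progression or death before the first post-baseline assessment, and it would be redundant if a baseline scan already qualified. Best overall response is likewise limited to post-baseline scans. The intended meaning is probably that of Protocol 9.3. That stands as evidence of intent, but the written rule still admits type D.

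It is also fair that the SAP wording errs low, that the shifts sit well inside the confidence intervals, and that ORR and CBR are secondary and descriptive. Nor does literally every subject have a baseline scan: SAP Tables 5 and 6 provide for its absence.

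Two stronger readings are tempting, and the documents do not support them.

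- A reader might infer from "The efficacy analysis will be based on the All Treated population and/or Efficacy Evaluable population, as appropriate" that the population could be chosen after seeing the result. The endpoint sections of the SAP commit to both populations, and planned Tables 14.2.1 to 14.2.4 show solid-tumor ORR in each. CBR has no separately titled table, so there the commitment rests on SAP 8.4. Only emphasis is left open. The summary of changes for Amendment 03 (Protocol 16.11) also records removal of the statement that the evaluable set was primary, so the lack of a lead population looks deliberate.
- A reader might take the Protocol Section 8 rates (2/11, 3/10) as the size of the problem. No planned table uses that definition. The same summary shows the 8-week wording being struck from 9.3, so the Section 8 sentence looks like a leftover.

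**Conclusion.** The point holds as a limited wording defect. SAP Table 3 departs from Protocol 9.3 without declaring it, and followed literally it adds non-responders to the Efficacy Evaluable denominator. The dilution is about 1 percentage point in the first illustration (13.3% against 14.3%) and 3.6 in the second (21.4% against 25.0%); it is zero if no subject with 3 doses leaves unscanned without an event. These sizes rest on assumed subject counts and on the literal reading.

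The SAP wording lowers the rate; it does not inflate it. The All Treated ORR and CBR do not change. The Protocol Section 8 sentence genuinely conflicts with 9.3 but drives no planned output.

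**What to change.** In SAP Table 3, insert post-baseline before the first mention of disease assessment, so that Efficacy Evaluable matches Protocol 9.3. No entry in SAP Section 12 is then needed. In Protocol Section 8, replace the sentence tying evaluability to the 8-week assessment with a reference to the 9.3 definition.

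Bracketing the and/or in both definitions would also settle whether early progressions and deaths with fewer than 3 doses count.

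Optionally, state in SAP Section 8 that All Treated leads for ORR and CBR and that Efficacy Evaluable is supportive. This would help readers weigh two reported rates, but the correction does not depend on it.

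The cost is wording only, with no new data, and is best paid before database freeze. The Efficacy Evaluable N may fall slightly, and its ORR and CBR would then stay the same or rise slightly.
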